**NCT02698163**

**Study Protocol in Submitted UCLA IRB#15-002015 (March 4th, 2020)**

## **Summary:**

Non-surgical root canal therapy (RCT) represents a standard of treatment that addresses infected pulp tissue in teeth and protects against future infection while preserving the tooth for the patient. RCT involves removing dental pulp comprising blood vessels and nerve tissue, followed by the placement of filler material to occupy the naturally occurring space where the pulp was removed. Currently, standard of care treatment for RCT utilizes gutta-percha (GP) as the root canal filling material. Tooth extraction is necessary if the RCT fails or if the tooth fractures. The need for extraction after failed RCT might be reduced by increasing the strength of the canal filling material closer to that of dentin. Nanodiamonds (NDs) may offer unique advantages due to their favorable properties, particularly for dental applications. In this prospective pilot study, we will utilize gutta-percha modified with nanodiamonds 5 wt % (NDGP) as the root canal filling material. Our research group has previously demonstrated NDGP's improvement in tensile strength compared to those of gutta-percha. We hypothesize that NDGP will not have a negative effect on clinical outcome for the patient compared to the GP. Additional potential positive benefits include decrease in void space and better clinician handling of NDGP during the canal filling procedure. NDGP with its increased mechanical properties, potential decrease in void space between the NDGP and the tooth's root, and the ease of handling by clinician of NDGP during vertical obturation procedure may result in a decrease in the pain experienced by the NDGP patients compared to those experienced by the control (GP) patients. Patients will be recruited and randomized into two RCT filler material patient groups for this study: 15 patients for the control, 15 patients with NDGP. For all the patients into the control arm of the study, the root canals will be filled with GP at the bottom third up to and including the top third, using a standard procedure involving vertical condensation obturation. For all the patients into the treatment arm of the study, the root canals will be filled with GP at the bottom third, NDGP in the middle third, and again with GP at the top third, using the vertical condensation obturation technique. The tooth will be restored with a crown for posterior teeth, or a composite filling for anterior teeth. There will ideally be a total of four visits: consultation appointment (~1 hour), RCT appointment (~2-3 hours), 6 month follow-up appointment (~1 hour), and 1 year follow-up appointment (~1 hour). Additional follow-up appointments (~1 hour) prior to the 6 month and 1 year follow-up appointments may be required in the event of infection or persistent pain of the root canal. Patient data will be categorized by age, weight, gender, and use of other drugs which may alter the pain assessment and pilot study success indicators. This study investigates a new type of filler, gutta-percha modified by the addition nanodiamond material (NDGP), which may be stronger and prevent complications of RCT such as tooth fracture to improve treatment outcomes.

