
## **Study Protocol:**

[name] will recruit the patient for this study after the patient's referral to the UCLA endodontics department for root canal therapy. Informed consent will be obtained by [name] from all the patients that will be able to be taken home for patients to consider being part of this pilot study. We will stress to the patient that there will be an intended benefit and that we will be providing an incentive for joining this study (parking vouchers). The sample population will be screened and collected [name], M.S.,

Ph.D., D.D.S. All of the patients must be over 18 years of age when the treatment commences. Teeth will be excluded from this study if they had preoperative periodontal disease, prior non-surgical and surgical endodontic treatment, or if the apex/apices under investigation is/are not discernible in any of the periapical radiographs. The teeth that will be excluded from the analysis of the 'periapical status following treatment' are if: (1) they were not followed-up for at least 6 months, (2) if they were extracted for reasons not related to endodontic problems (for e.g. periodontal disease), (3) information on the periapical status during the time of extraction was not available.

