oxide-eugenol (Kerr Corporation, Orange, CA, USA). After the root canal treatment is done, the patient will be treated by [name], a general dentist for the restorative aspect of the procedure. Depending on how much tooth structure is left, he will decide which kind of build-up material to use and if a post is needed. The tooth will be restored with a crown for posterior teeth, or a composite filling for anterior teeth.

The goal is to follow-up all treated teeth 6 months and 1 year post-RCT. Appointment letters will be mailed to the patients 1 month prior to the follow-up dates. Patients, who failed to attend for recall, will be contacted with a personal courtesy call by the study team member (dentist on study team) and a more detailed explanation letter will be mailed to encourage them to attend follow-up appointments. If patients continue to not attend for recall, then the reasons provided by each patient (if provided) will be recorded. Recall appointments can be made as necessary other than the 6-month and 1-year follow-up appointments. Recall appointments will have their own specific form detailing the patient's reason and required procedure. Possible complications will be communicated to the patient prior to the study and will be dealt with on a case by case basis.

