The root canal therapy (RCT) procedure has potential risks and complications associated with the procedure: possible pain swelling, separation of instrument, perforation, fracture/crack, requirement for permanent restoration, and extraction of tooth if persistent infection is observed. If the tooth is indicated for an extraction instead, the extracted tooth will be evaluated for other potential causes of failure (eg. cracked tooth, missed extra canals, difficult canal anatomy, etc.). Extractions should be considered upon the identification of a fractured and cracked tooth during an apicoectomy. After the root canal therapy, if pain or pressure persists for more than a few days after the RCT, the endodontist would need to evaluate the prognosis of the tooth and determine whether the tooth is viable or needs extraction due to inadequate infection control of the canal or damage to tooth structure during the RCT. An extraction may also be indicated several years after the RCT due to persistent infectious bacteria or microleakage of the endodontically treated tooth. Other indications for extractions include perforations, coronal breakdown, or periodontal disease. If a tooth were to be extracted due to endodontic problems, such as persistent pain, swelling, sinus or periapical lesion, the treatment will be considered as a failed outcome. Tooth extraction without any information on postoperative periapical status will be excluded from analysis. We have to keep in mind that even conventional RCTs do not have a 100% success rate. Most studies say that primary RCTs have about a 86% success rate - so when taking that into consideration, we cannot assume that if the procedure fails, it is due to the NDGP material.

Customized forms, recorded by endodontic postgraduate students, will be used for recording follow-up information and radiographic assessments. The patient's medical conditions will be self-reported onto a standard medical history form at the first appointment and will be verified and updated by interview prior to the both arms of control and treatment and at the follow-up appointment. While all conditions reported by the patient will be recorded, only those that will be common among the patients or previously reported to have significant association with treatment outcome will be further analyzed.

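### Two rules for extracted teeth conflict in one narrow case: a follow-up reading exists, none was taken at extraction, and the reason was endodontic or unknown

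*Combined protocol and SAP*

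**What the plan says.** The exclusion list near the start of the Study Protocol section has a stated scope: "The teeth that will be excluded from the analysis of the 'periapical status following treatment' are if". Its first two items are "1) they were not followed-up for at least 6 months, (2) if they were extracted for reasons not related to endodontic problems", and its third is "3) information on the periapical status during the time of extraction was not available".

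The paragraph on complications and extraction, later in the same section, gives two further statements. For a tooth extracted because of endodontic problems, it says "such as persistent pain, swelling, sinus or periapical lesion, the treatment will be considered as a failed outcome", with no condition about a reading at extraction. It then says "Tooth extraction without any information on postoperative periapical status will be excluded from analysis", without naming the analysis.

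Readings are planned at two visits: "The goal is to follow-up all treated teeth 6 months and 1 year post-RCT". The protocol judges treatment success on two measures: absence of apical periodontitis, and tooth survival. The Statistical Analysis section covers only the mechanical tests of the material and defines no clinical analysis set.

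**The concern.** The two paragraphs ask for information from different periods. The exclusion list wants periapical status as it stood at extraction. The later paragraph is satisfied by postoperative information from any time. A 6-month radiograph meets the second condition and not the first.

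The situation is foreseeable. A tooth can be read at 6 months and extracted elsewhere before 1 year, and the team may learn of this only when it contacts a patient who missed recall. A tooth extracted for an endodontic reason is a failure by the protocol's own definition. If the exclusion list is followed, that failure leaves both numerator and denominator of the periapical success rate, and the rate rises in whichever arm it occurs. The trial hypothesis is that the nanodiamond material does no clinical harm, so a lost failure in that arm would favour the hypothesis. As nothing says which rule governs, the choice stays open until someone meets such a tooth, and by then its outcome would be known.

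**Working it through.** There is no stated figure to reproduce, so the first step is to set the rules side by side for extracted teeth.

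| Extracted tooth | Third exclusion item | All three items together | Later paragraph |
|---|---|---|---|
| Endodontic reason, at least 6 months' follow-up, follow-up reading, status at extraction known | not excluded | not excluded | not excluded; failure |
| Same, but status at extraction not known | excluded | excluded | not excluded; failure |
| Reason unknown, at least 6 months' follow-up, follow-up reading, status at extraction not known | excluded | excluded | not excluded; outcome not stated |
| Non-endodontic reason, follow-up reading, status at extraction not known | excluded | excluded, by item (2) in any case | no matching exclusion |
| Endodontic reason, no postoperative reading at all | excluded | excluded | excluded by one sentence, failure by another |

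The third item makes the difference in rows two and three. In row four, item (2) removes the tooth whatever item (3) says. Row five shows that the later paragraph also needs tidying. An endodontic extraction before 6 months meets a separate ground, item (1), which likewise sits beside the failed-outcome statement without being reconciled with it.

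The second step is to size the effect of one such tooth. Inputs:

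- n = 15 per arm, from the Summary: "15 patients for the control, 15 patients with NDGP". One tooth per patient is assumed.
- Background success rate, from the Study Protocol section: "Most studies say that primary RCTs have about a 86% success rate". Expected successes are 0.86 × 15 = 12.9, so take s = 13.
- k = number of teeth of this kind in the arm. The documents give no value; k = 0 is possible.

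The rate with the teeth kept as failures is s/n; with them dropped it is s/(n − k). The shift is s/(n − k) − s/n.

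- s = 13, k = 1: 13/15 = 86.7%; 13/14 = 92.9%; shift 6.2 points.
- s = 12, k = 1: 12/15 = 80.0%; 12/14 = 85.7%; shift 5.7 points.
- k = 0: no shift.

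For scale, the standard error of one arm's rate is √(0.86 × 0.14 / 15) = 0.090, or 9.0 points. One dropped failure moves the estimate by 6.2/9.0, about 0.7 standard errors.

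**The case against.** The strongest reply is that both sentences are exclusion rules. The later one gives one ground for leaving a tooth out and does not promise to keep every other extracted tooth, so a wider exclusion could stand beside it. Taken alone, that is a fair reading. It does not dispose of the point, because the same paragraph also calls extraction for endodontic problems a failed outcome without requiring a reading at extraction. A tooth cannot be both a failure and excluded from the same success measure.

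The later sentence might also refer to some other analysis, since it names none. The documents do not say so, and its own criterion is periapical status.

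Three limits do stand. First, a reader might infer that any extracted tooth with a 6-month reading is treated in opposite ways. That is not so: the rules agree when status at extraction is known, and item (2) settles non-endodontic extractions. The case narrows further if the recorded reason was a periapical lesion, since that is arguably periapical information at extraction. Second, a reader might infer that extractions disappear from the results. The exclusion list is confined to periapical status, and nothing in it removes a tooth from the survival measure. Third, a reader might take the extreme case, in which both failures in an arm are of this kind and 13/15 becomes 13/13 = 100%, as the size of the problem. That needs every failure in the arm to be extracted without a record, and the documents give no support for such a count. The protocol also foresees retreatment after some failures and examination of extracted teeth, both of which make the case less common.

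**Conclusion.** The inconsistency is real and narrow. It concerns a tooth with a follow-up reading, extracted later for an endodontic or unknown reason, with no periapical status at extraction. The exclusion list drops it; the later paragraph does not exclude it and, where the reason was endodontic, makes it a failure. Followed as written, the third exclusion item can remove a failure from the first success measure and raise that arm's rate. It leaves tooth survival alone.

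The 6.2-point shift is an illustration. It rests on one tooth per patient, 13 successes among 15 and exactly one affected tooth; the true number may be zero. The protocol states no clinical test, so no planned comparison can be shown to change, and nothing in the documents suggests an intention to choose the rule after seeing results. The matter is worth correcting because, with 15 teeth in an arm, one is enough to show and the correction is cheap.

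**What to change.** Replace the third exclusion item with one rule, name the analysis it governs (periapical status following treatment), and fix it before outcome data are examined:

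- A tooth extracted for an endodontic reason counts as a failure from extraction onward, whether or not a reading was taken at extraction. State that this holds for extractions before 6 months too, so that item (1) does not remove them.
- Any follow-up reading counts at the visit where it was taken. The immediate post-obturation radiograph is not a follow-up reading; otherwise almost every treated tooth would qualify.
- Item (2) continues to govern extractions for non-endodontic reasons.
- A tooth is excluded under this rule only if it has no follow-up periapical reading and the reason for extraction is unknown. Where the reason is unknown but a follow-up reading exists, the tooth contributes that reading; the rule should say how its later visit is reported.

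Bring the exclusion sentence in the complications paragraph into line with this wording. The cost is a short text change in two places and no new data. The downside is that the reported periapical success rate may be slightly lower.

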**Patients will be excluded if they are** currently taking medications used to treat osteoporosis or currently taking any form of IV bisphosphonates, allergic to dental materials, have dental phobia, have MD consult/medically compromised/prophylaxis needed, have any developmental/congenital disorders, have mentally unstable/psychological issues, have any craniofacial disorder/syndromic cases or have a low pain tolerance/inquire about past dental experience. Patients will be also excluded if they had any of the following periodontal complications: current moderate to severe periodontitis (history is ok), greater than 4mm pocket depths, mobility of the tooth, furcation involvement, less than 4 month recall status, periodontal surgery needed and poor periodontal diagnosis around tooth of concern (ie. tooth may need to be extracted). Patients will also be excluded if they had any of the following restorative complications: tooth is non-restorable, has severe abfraction, has severe attrition, severe bruxism or history of severe bruxism and insufficient tooth structure (ie. post is needed). Patients will be excluded if they have any of the following endodontic complications: endodontic treatment needed on third molars, open apices, complicated root canal anatomy including sharp curvature, C-shaped canal, pulp stones/calcification, previous RCT/initiated pulp therapy, previous apical surgery, lateral lesion, root fracture, severe crown fracture (requiring post), perforations, non-endodontic related pathology, periapical radiolucency (minimum size to be determined by [name]), external/internal root resorption and surgical root canal procedure. Patients will be excluded if they have poor oral hygiene, diet, history or current drug use, and complicated dental history.

The main operator will be [name], DDS. He is a Resident in the Section of Endodontics. [name], D.D.S. will be an advisor to the study. He is a Professor of Clinical Dentistry and Chair of the Section of Special Patient Care and is the Vice Chair of the Division of Advanced Prosthodontics. [name] is the Program Director of the General Practice Residency Program at UCLA. He also received his undergraduate at UC Berkeley, and he received his dental and GPR degrees from UCLA.

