Primary root canal treatment will be provided to teeth that did not have prior non-surgical and surgical endodontic treatment. Standard principles of primary RCT consistent with the American Dental Association Guidelines will be followed, and the treatment protocol will be consistent with UCLA Department of Endodontics treatment protocol. All treatments will be performed under both local anesthesia and rubber dam isolation to ensure absence of saliva leakage. Sodium hypochlorite solution will be used as an irrigant during the whole procedure. The location of the apical terminus will be aided by an electronic apex locator. The initial working length will be determined by taking a radiograph with the diagnostic file placed at the maximal extent achievable with the smallest file. The initial size of the file (recorded as Initial Apical File (IAF)) will be

the largest that could reach the radiographic apex without force to ensure good electrical contact and stability when taking the radiograph. The apical instrumentation will be determined by the operator as a distance equal or slightly shorter (<0.5mm) than the working length.

The operator, [name], DDS will be choosing his own various types of instruments and techniques for canal negotiation and shaping. The instruments available for use include: (i) K-flex files (Dentsply Maillefer, Ballaigues, Switzerland), (ii) Flex-O-files (Dentsply Maillefer), (iii) Hedström files (Dentsply Maillefer), (iv) GT hand instruments (Dentsply Maillefer), (v) ProTaper hand instruments (Dentsply Maillefer), (vi) rotary GT instrument system (Dentsply Maillefer), (vii) rotary ProFile instrument system (Dentsply Maillefer), (viii) rotary ProTaper instrument system (Dentsply Maillefer) and (ix) rotary K3 instrument system (SybronEndo). The stainless steel instruments will be used in push-pull filing (Abou-Rass et al. 1980), stem-winding (Backman et al. 1992) or balanced-force (Roane et al. 1985) motions. Patency will be maintained during canal shaping and filing by placing a small file of size 8 or 10 passively to 0.5 mm beyond the apex, between each instrumentation step during the canal enlargement. The recommended minimum or optimal apical size of canal preparation is a size 30 with a taper of 0.06.

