5.25% Sodium hypochlorite (NaOCl) solution will be the standard root canal irrigant. Root canal preparation cream (Premier, Plymouth Meeting, PA, USA) will be used as an intracanal lubricant if needed. Calcium hydroxide (Ca(OH)2) will be the standard interappointment medicament for teeth with acute pulpitis if removal of pulp tissues at the first visit was incomplete.

Patients will be randomized according to a predetermined order created by [name] and [name] via Matlab. 30 patients will be assigned a number 1-30 according to the order of recruitment for this study 1 being assigned to the first patient recruited and 30 to the last patient recruited for this study. The randperm(30,15) function will be used to create a list of 15 numbers from the 30 (recruitment order number). This list of 15 numbers (recruitment order numbers) will be the Nanodiamond gutta percha (NDGP) group to receive the NDGP filler material. The remaining 15 numbers will be given the standard of care gutta-percha filler material. This list will be arranged accordingly for the clinicians' reference.

For all the patients into the control arm of the study, the root canals will be filled with gutta percha at the apical third up to and including the coronal third, using the vertical condensation obturation technique, also known as the modified Schilder's warm vertical compaction technique (Van Zyl et al. 2005). The root canal sealer used will be zinc oxide-eugenol (Kerr Corporation, Orange, CA, USA). After the root canal treatment is done, the patient will be treated by [name], a general dentist for the restorative aspect of the procedure. Depending on how much tooth structure is left, he will decide which kind of build-up material to use and if a post is needed. The tooth will be restored with a crown for posterior teeth, or a composite filling for anterior teeth.

For all the patients into the treatment arm of the study, the root canals will be filled with gutta percha at the apical third, Nanodiamond gutta percha (NDGP) in the middle third, and again with gutta percha at the coronal third, using the vertical condensation obturation technique, also known as the modified Schilder's warm vertical compaction technique (Van Zyl et al. 2005). The root canal sealer used will be zinc

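### The full assignment list is drawn in advance, keyed to recruitment order and given to the clinicians with no concealment, so the next arm can be known before eligibility is judged

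*Combined protocol and SAP*

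**What the plan says.** The randomisation paragraph of the Study Protocol sets out a predetermined order made in Matlab. It states that "30 patients will be assigned a number 1-30 according to the order of recruitment for this study", with 1 for the first patient and 30 for the last. One call to randperm(30,15) picks the 15 numbers that receive nanodiamond gutta-percha (NDGP); the other 15 receive standard gutta-percha. It ends: "This list will be arranged accordingly for the clinicians' reference". It does not say which clinicians receive the list, or when. The text supplied mentions no envelopes, no third-party release, no restricted access and no rule on when the arm is revealed.

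Three other parts of the Study Protocol bear on this:

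- **Eligibility.** Some exclusions rest on judgement without a threshold. One list ends "or have a low pain tolerance/inquire about past dental experience"; another ends "history or current drug use, and complicated dental history".
- **Canal preparation.** The operator, "DDS will be choosing his own various types of instruments and techniques for canal negotiation and shaping", works from a stated set of instruments.
- **Obturation.** The treatment arm has gutta-percha in the apical third, NDGP in the middle third, and "again with gutta percha at the coronal third". Technique, sealer and restoration are described identically for both arms.

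**The concern.** Randomisation guards against selection bias only if the next assignment is unknown when someone decides whether a patient enters. Under the current wording, a clinician holding the list could, knowingly or not, apply a loosely defined exclusion more strictly when the next number belongs to one arm. The open criteria are not remote from the outcome: treatment success requires absence of pain, and low pain tolerance is one of the exclusions without a cut-off.

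The same knowledge is available while the canal is prepared. The operator chooses the instruments and techniques, and the protocol itself names insufficient instrumentation as a cause of failure. If case selection or preparation followed the arm, a difference between arms could not be attributed to the filler alone.

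**Working it through.** **1. The plan's own split.** randperm(30,15) returns 15 distinct numbers from 1 to 30 and leaves 15. So 15 + 15 = 30, which agrees with the 15 and 15 in the Summary.

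**2. With the list in hand.** The arm is a fixed function of the recruitment number. Someone who knows how many patients have been recruited knows the next number and so the next arm: 30 of 30, or 100%.

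**3. List concealed, past assignments remembered.** Because the total is fixed at 15:15, the best guess is always the arm with more places left. With a and b places left, the expected number of correct guesses is

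E(a,b) = max(a,b)/(a+b) + [a/(a+b)]·E(a−1,b) + [b/(a+b)]·E(a,b−1), with E(0,0) = 0.

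This gives E(15,15) = 17.961. The closed form with m = 15 agrees:

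m + 2^(2m−1)/C(2m,m) − 1/2 = 15 + 536,870,912/155,117,520 − 0.5 = 15 + 3.461 − 0.5 = 17.961.

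Accuracy is 17.961/30 = 59.9%. On average, the last 1.875 assignments are certain to such a person because one arm is already full.

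**4. List concealed, past assignments not known.** Each number has probability 15/30 = 50% of being NDGP.

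**5. When the arm is first needed.** The described arms differ only in the middle-third filler, so nobody needs the assignment before obturation. Knowledge during eligibility assessment and shaping is therefore avoidable; knowledge by the operator at obturation is not.

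**6. Extra recruits if assignment waits for obturation.** If a share f of recruits never reaches that step, filling 30 packets takes 30/(1−f) recruits. The documents give no rate, so f is assumed: f = 0 gives 30; f = 5% gives 31.6, so 32; f = 10% gives 33.3, so 34.

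**The case against.** The best defence is that the clinicians meant may be only the treating ones. The person who screens is listed with different degrees from the operator, who is described as a resident, so they may be different people, and the list may reach the operator late. That is possible, but the wording limits neither the recipients nor the timing, and names are removed, so any overlap among recruiter, screener, operator and list creators cannot be checked. If restricted release is the intent, writing it down is the remedy.

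It is also fair that the operator cannot be kept unaware of the filler. This stands for obturation and afterwards, but not for the steps before it. The preparation route is the weaker of the two: treatment must follow the department's protocol, a recommended preparation size is given, and the documents show no motive for varying instruments by arm.

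This is a 30-patient pilot, which limits how much weight the point should carry. Patients are still randomised so that clinical outcomes can be compared.

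A reader might infer that enrolment was steered or that the result will be biased. The documents do not support that: they show an unprotected step, not its misuse. A reader might also think that recorded baseline and treatment data, such as the file size "recorded as Initial Apical File (IAF", would settle the matter. The plan proposes no such comparison, and an imbalance would not show its cause. Masking of the restoring dentist and the follow-up examiner is a separate question, not raised here.

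**Conclusion.** The point holds as a cheap improvement. The protocol fixes every assignment in advance, keys it to recruitment order and hands the list to clinicians without concealment, so a holder can know the next arm with certainty instead of guessing it at 50% to 59.9%. The exposure covers eligibility decisions that depend partly on judgement and, less strongly, canal preparation.

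This rests on two conditions. Absence of concealment is judged on the text supplied, from which some pages and all names were removed. The 59.9% assumes the fixed 15:15 split and someone who recalls every earlier assignment. No amount of bias can be derived from the documents, and none is asserted.

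**What to change.** Replace the sentence that gives the list to the clinicians, and amend the sentence that numbers patients by recruitment, with its two bracketed echoes in the randperm text. Suggested wording:

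> Numbers 1-30 are given in the order in which patients are assigned. The list is created and held by existing team members who do not recruit, screen, treat or examine patients. They supply 30 sequentially numbered, sealed, opaque packets, each holding a slip that names the assigned arm. The next packet is assigned, dated and opened only after consent, confirmed eligibility and completed shaping, immediately before obturation. Recruiters, screeners, and the operator before obturation, do not see the list. Each patient whose packet is opened stays in the assigned arm for comparison; the exclusions from analysis stated elsewhere in this protocol are unchanged.

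The essential part is that no packet is opened before consent and confirmed eligibility. Waiting until shaping is complete also protects canal preparation. The protocol foresees a second visit in some cases, since calcium hydroxide "will be the standard interappointment medicament for teeth with acute pulpitis if removal of pulp tissues at the first visit was incomplete"; the packet is then opened at the visit where obturation takes place.

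The costs:

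- The wording changes above and 30 packets. The randperm draw and the 15:15 split stay as they are.
- Filler for both arms must be available at the chairside.
- Patients who do not reach obturation no longer use a number. This changes who counts as randomised, and 30 to 34 recruits would be needed if 0 to 10% do not reach it (an assumed range).
- The sponsor must confirm that the two list creators, and whoever holds the list, have no recruiting, screening, treating or examining role. Otherwise the list should be redrawn by someone who has none.
- Some predictability remains: an operator who remembers past assignments can still guess the next one 59.9% of the time.
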